#### Primary Outcome

-Proportion of patients transfused at least 1 unit of packed red blood cells during hospital admission

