#### Secondary Outcomes

-Mean number of units transfused per patient

-Calculated blood loss

-Incidence of symptomatic VTE diagnosed within 6 months of surgery

- Wound complications diagnosed within 6 months of surgery
- MI diagnosed within 6 months of surgery
- CVA diagnosed within 6 months of surgery
- All-cause mortality at 6 months

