### Analysis

The primary outcome will be the proportion of patients transfused at least 1 unit of packed red blood cells during hospital admission. Secondary outcomes will include mean number of units transfused per patient, calculated blood loss, and incidence of adverse events at six months including: VTE, MI, CVA, wound complications, and all-cause mortality as previously defined. The cohort of patients treated with early administration of TXA in the ED will be compared to a control group who were not treated with TXA at any point. All outcomes will be reported descriptively using appropriate summary statistics, including 95% confidence intervals, where appropriate. Baseline variables, including fracture type, surgical procedure, presenting hemoglobin, history of coronary artery disease, American Society of Anesthesiologists (ASA) score, length of surgery, length of anesthesia and type of anesthesia will be summarized overall and separately by study group; because this is a prospective, randomized trial, no formal between-group comparisons of baseline covariates will be performed. Adverse events as well as the primary and secondary outcomes occurring during the hospital stay and up to six months following surgery will be evaluated using chi-square tests and logistic regression (for categorical variables) if complete follow-up is obtained for the study subjects. If follow-up varies because of subject withdrawal or lack of response at 6 months, these outcomes will be estimated and evaluated using survivorship methods such as Kaplan-Meier estimation and Cox proportional hazards regression. Two-sample t-tests will be used to compare continuous variables between the study groups. All statistical tests will be two-sided and the threshold of statistical significance will be set at  $\alpha = 0.05$ .

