### Sample Size

In a prospective randomized, controlled trial conducted in Denmark evaluating a similar outcome in the same patient population, there was a transfusion rate of 84.6% in the control group, who never received

TXA [9]. However, a retrospective evaluation of the transfusion rate for the population of interest at our institution in 2014 with standard transfusion thresholds as reflected in the above described protocol was 50%. Utilizing this transfusion rate, the sample size was calculated to be able to detect a difference of 50% versus 25% (a reduction of risk by 1/2) between the control group and treatment group, respectively. A sample of 58 subjects per study group (116 in total) will provide 80% power to detect a difference in the proportion of patients receiving blood transfusion of 50% versus 25% ( $\alpha=0.05$ , two-sided test) [10]. We will assume an attrition rate of at least 15%, thus the target sample size will be 78 patients per group, 156 in total.

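### As written, the test of the in-hospital primary outcome depends on complete 6-month follow-up, and the plan's own attrition assumption points to the time-to-event fallback

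*Combined protocol and SAP*

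**What the plan says.** All references are to the combined protocol and SAP.

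- **Primary Outcome:** "Proportion of patients transfused at least 1 unit of packed red blood cells during hospital admission". This is binary and known by discharge.
- **Secondary Outcomes:** the event outcomes have their own longer window, for example "Incidence of symptomatic VTE diagnosed within 6 months of surgery".
- **Analysis, first branch:** the sentence opens with "Adverse events as well as the primary and secondary outcomes occurring during the hospital stay and up to six months following surgery" and assigns these to chi-square tests and logistic regression, as categorical variables, "if complete follow-up is obtained for the study subjects".
- **Analysis, second branch:** when follow-up varies through withdrawal or "lack of response at 6 months, these outcomes will be estimated and evaluated using survivorship methods such as Kaplan-Meier estimation" and Cox regression.
- **Analysis, continuous outcomes:** "Two-sample t-tests will be used to compare continuous variables between the study groups". No follow-up condition is attached here.
- **Sample Size:** 58 per group "will provide 80% power to detect a difference in the proportion of patients receiving blood transfusion of 50% versus 25"%, two-sided at 0.05. Then "We will assume an attrition rate of at least 15"%, with a target of 78 per group, 156 in total.
- **Clinical Follow-up:** the only follow-up period defined anywhere is six months, counted from surgery.

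**The concern.** The condition in the first branch is put on the subjects as a whole, not on each outcome over its own window. The outcomes it covers explicitly include the primary, so the fallback's reference back to those outcomes includes it too. No other sentence gives the binary primary an unconditional test.

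Whether a patient answers a call at six months has no bearing on whether that patient was transfused during the admission. A rule that lets the first decide how the second is tested has no statistical rationale.

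What is at stake is the estimand. The proportion asks whether a patient is transfused at all; Cox regression and the log-rank test also use when. If TXA only postponed the first transfusion, with the same share transfused by discharge, the time-to-event analysis could count the delay as benefit and the proportion would not. At the least, the text leaves two defensible primary tests open after the data are seen.

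**Working it through.** **1. Which test the trial is sized on.** Inputs from Sample Size: p₁ = 0.50, p₂ = 0.25, two-sided α = 0.05, power 80%. With pooled variance under the null and no continuity correction:

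n = [1.960·√(2·0.375·0.625) + 0.842·√(0.25 + 0.1875)]² / 0.25² = (1.342 + 0.557)² / 0.0625 ≈ 57.7, so 58 per group.

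Power at 58 per group is 80.2%. The plan's figure is reproduced as a comparison of two proportions, which is the chi-square branch.

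**2. Which branch would apply.** With N = 156 and independent losses at rate d, P(complete follow-up) = (1 − d)^156.

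| Loss rate d | Expected lost | P(all 156 followed) |
|---|---|---|
| 15% (the plan's minimum) | 0.15 × 156 = 23.4 | 9.8 × 10⁻¹² |
| 5% (assumed) | 7.8 | 0.03% |
| 2% (assumed) | 3.1 | 4.3% |
| 1% (assumed) | 1.6 | 21% |

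The plan does not say whether its attrition falls before discharge or by six months. That matters little here: read literally, one withdrawal or one 6-month non-responder ends complete follow-up.

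**3. What the switch does to the primary.** The documents give no transfusion times, so these are assumed. First transfusion occurs at 0.1 day plus a gamma variable (shape 2, mean 1.5, 2.0 or 2.5 days), with a constant delay on TXA where stated. Patients never transfused are censored after the last in-hospital event. There are 78 per arm and 40,000 simulated trials per scenario. The log-rank test stands for the Cox comparison, being its score test. Ranges run over the three means.

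| Final proportions, control v TXA | TXA delay | Log-rank rejects | Share of those rejections favouring TXA |
|---|---|---|---|
| 50% v 25% | none | 89.9–90.3% | – |
| 50% v 50% | none | 4.9–5.1% | – |
| 50% v 50% | 0.25 day | 5.3–5.7% | 65–76% |
| 50% v 50% | 0.5 day | 6.3–7.4% | 78–88% |
| 50% v 50% | 1 day | 8.6–13.5% | 92–97% |

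Chi-square rejects in 90.8–91.1% of trials at 50% v 25% and in 4.4–4.7% in every 50% v 50% row. Exact calculation for the uncorrected chi-square at 78 per arm gives 90.9% and 4.5%.

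**4. A second timing model.** First transfusion is uniform over days 1 to 4, 78 per arm, 1,500 trials per scenario, with non-transfused patients censored either at discharge or during six months of follow-up. At 50% v 50% with a one-day TXA delay, log-rank rejects in 11.1–12.2% and chi-square in 4.1–4.8%. With equal timing the two tests disagree on significance in 1.8–2.5% of trials.

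**The case against.** The strongest reply is that the literal reading proves too much. The same list of outcomes takes in units per patient and calculated blood loss, which nobody would test by chi-square or analyse as ordinary time-to-event data. The list is plainly loose. The fallback is also triggered by follow-up that varies, and follow-up for an in-hospital outcome does not vary because someone is unreachable at six months. The Sample Size section answers attrition by recruiting more patients for a comparison of proportions, which would make little sense if any loss moved the primary to Cox regression. No time origin or censoring rule is given for transfusion. In addition, the harm shown needs a TXA-only delay that the documents do not mention. If no patient is censored before the last in-hospital transfusion, the final Kaplan-Meier estimate equals the raw proportion, so only the Cox comparison differs.

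Much of this stands. It is good evidence of intent, and it limits the size of the problem. It does not supply the missing statement. Units and blood loss are rescued by the separate t-test sentence; the binary primary has no such sentence and is named in the conditional one. The lack of a time origin and censoring rule also means that the fallback, if applied to transfusion, could not be carried out as specified.

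**Conclusion.** The concern holds on the text as written. The plan ties the test of an in-hospital proportion to six-month contact, and at its own attrition of 15% or more the chi-square branch has practically no chance of applying (about 10⁻¹¹, assuming independent losses).

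The result is a change of estimand, not a loss of power or a miscalibrated test. With equal timing in the two arms the numerical effect is negligible. It becomes material only if TXA delays first transfusion without reducing the final proportion: log-rank rejection reaches 8.6–13.5% for a one-day delay, and at most 7.4% for half a day. Those figures rest on assumed timing. Confidence is moderate because the authors may well have meant the fallback only for the 6-month events. Even so, the primary test should be stated without ambiguity, and this should be fixed.

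**What to change.** In the Analysis section:

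1. Add a sentence that the primary outcome is tested as binary, by chi-square test or logistic regression, in all randomised patients regardless of 6-month follow-up. Patients discharged, or dying in hospital, without a transfusion are counted as not transfused.
2. Limit the Kaplan-Meier and Cox sentence to the 6-month event outcomes: VTE, MI, CVA, wound complications and all-cause mortality.

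Optional, and not needed to resolve the ambiguity: report the risk difference with its 95% confidence interval, and add a best-case/worst-case sensitivity analysis for patients who withdraw before discharge, the only group whose primary outcome could actually be missing through withdrawal.

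The cost is one sentence and one limiting clause. No new data are needed and the sample size does not change: it already rests on a comparison of proportions.

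### The six-month fallback names Kaplan-Meier for VTE, MI, CVA and wound complications without addressing death as a competing event, so it modestly overstates their incidence in its usual form

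*Combined protocol and SAP*

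**What the plan says.** The Secondary Outcomes section lists each non-fatal event as a six-month incidence, for example "Incidence of symptomatic VTE diagnosed within 6 months of surgery". All-cause mortality over the same six months is a separate item, and no composite with death is defined.

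The Analysis section gives two routes for these outcomes. The first is "chi-square tests and logistic regression (for categorical variables) if complete follow-up is obtained for the study subjects". The second applies when follow-up varies because subjects withdraw or do not respond: "these outcomes will be estimated and evaluated using survivorship methods such as Kaplan-Meier estimation and Cox proportional hazards regression". That sentence does not separate mortality from the non-fatal events.

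The Sample Size section says "We will assume an attrition rate of at least 15" per cent. Neither competing risks nor cumulative incidence functions are mentioned anywhere in the document, and nothing says how a patient who dies without the event enters the analysis of that event.

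**The concern.** A patient who dies without a VTE can no longer have one. The complete-follow-up route counts that patient as event-free, so it estimates the incidence that actually occurs. Kaplan-Meier with deaths censored removes the patient from the risk set and gives each later event more weight. It therefore estimates the risk that would apply if death did not intervene.

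The outcome sections name the first quantity. Under the plan as written, a few missed contacts at six months could change which quantity is reported. The outcomes concerned are the six-month thrombotic and wound harms, which readers take as absolute risks, and a larger trial would not remove the difference.

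**Working it through.** **The plan's own figure.** The plan gives no figure for the six-month analysis. Its sample size is the only figure that can be reproduced. For 50% versus 25%, two-sided 0.05 and 80% power, the pooled-variance formula without continuity correction gives [1.96·√(2·0.375·0.625) + 0.8416·√(0.25 + 0.1875)]² / 0.25² = (1.342 + 0.557)² / 0.0625 ≈ 57.7, so 58 per group, as stated (power 80.2%). The present point does not depend on it. The check uses the target enrolment of 78 per arm.

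**Inputs.** From the documents: six months of follow-up, 78 per arm and 15% attrition (used here as six-month loss, which is an assumption). Assumed, because the documents give none: six-month mortality of 5% to 30%, non-fatal event incidence of 2% to 15%, and event timing.

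**Direction, by counting.** Take 78 patients with nobody lost, 12 event-free deaths, and then 7 events.
- Proportion: 7/78 = 9.0%.
- One minus Kaplan-Meier with deaths censored: 7/(78 − 12) = 7/66 = 10.6%.
- Ratio: 78/66 = 1.18. This is an extreme ordering, with every death before every event. If every event came before every death, the two figures would be equal.

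**Constant hazards.** Let *m* be the assumed six-month mortality, d = −ln(1 − m), and h the event hazard over six months.
- Actual incidence = h/(h + d) · [1 − exp(−(h + d))].
- One minus Kaplan-Meier tends to 1 − exp(−h).

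Example with m = 15% and actual incidence 10%: d = 0.1625, and solving gives h = 0.1145. Check: 0.1145/0.2770 · (1 − e^(−0.2770)) = 0.100. Kaplan-Meier then gives 1 − e^(−0.1145) = 10.82%.

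| Assumed mortality | KM reading, actual 5% | KM reading, actual 10% | Relative excess at 10% | Extra patients of 78 at 10% |
|---|---|---|---|---|
| 5% | 5.13% | 10.25% | 2.5% | 0.20 |
| 10% | 5.27% | 10.53% | 5.3% | 0.41 |
| 15% | 5.41% | 10.82% | 8.2% | 0.64 |
| 20% | 5.57% | 11.13% | 11.3% | 0.88 |
| 25% | 5.75% | 11.47% | 14.7% | 1.15 |
| 30% | 5.93% | 11.84% | 18.4% | 1.44 |

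The largest excess over the whole assumed range is 2.7 points, or about 2.1 patients per arm (30% mortality, 15% incidence).

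**Early events.** Put all events in month 1 and keep the death hazard constant over six months, so d = −ln(1 − m)/6 in that month. The relative excess is about 0.9%, 1.9% and 3.0% at 10%, 20% and 30% mortality. For an actual 10%, that is 10.09%, 10.18% and 10.29%.

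**Simulation with loss.** Constant hazards, 78 per arm, 15% uniform loss, 4,000 replicates, actual incidence 5%:

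| Assumed mortality | One minus KM | Aalen-Johansen | Crude proportion |
|---|---|---|---|
| 10% | 5.2% | 5.0% | 4.6% |
| 20% | 5.6% | 5.0% | 4.7% |
| 30% | 5.9% | 5.0% | 4.6% |

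Aalen-Johansen recovers the actual value. The crude proportion falls short because of the losses, so some fallback is needed. The sampling SD of the Aalen-Johansen estimate is about 2.6 points here, well above the Kaplan-Meier excess of 0.2 to 0.9 points.

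**Between arms.** With the same event hazard in both arms (h = −ln 0.9) and mortality of 10% versus 20%, Kaplan-Meier reads 10.0% in both. Actual incidence is 9.5% versus 9.0%.

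**The case against.** The fault is partly inferred from silence. The fallback wording is an open list that would admit a cumulative incidence estimator, and the plan never says that deaths are censored. A reader might infer that Kaplan-Meier can only censor deaths. That goes too far, since an event-free decedent can be kept in the risk set to six months, or death can be made part of a composite. It remains true that the plan names Kaplan-Meier, that censoring deaths is its ordinary use, and that no alternative is specified.

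A reader might also infer that the fallback is certain to run. The 15% is an allowance in the sample size for an in-hospital primary outcome. It is not stated as six-month loss, and the Clinical Follow-up section adds telephone contact. The fallback is likely but not established.

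Nor do the documents support saying that every non-fatal rate will be biased, or that these are the only safety figures. The excess is zero in an arm where no event follows an event-free death, and in-hospital adverse events are also evaluated.

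The between-arm objection largely stands. Cox regression with deaths censored is a valid comparison of cause-specific hazards, and equal mortality inflates both arms alike. Cumulative incidence also has a weakness: higher mortality in one arm lowers its event incidence without any change in event hazard. That is a reason to read incidence alongside mortality by arm. It does not justify reporting a different quantity under the name of incidence.

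**Conclusion.** The concern holds as a modest, systematic overstatement, conditional on the fallback being used and deaths being censored. With constant hazards, the relative excess is about 2.5% to 15% over assumed mortality of 5% to 25%. It shrinks to about 1% to 3% (10% to 30% mortality) if events fall in the first month. In most scenarios this is under one patient per arm and smaller than sampling error. All of these sizes rest on assumed mortality, incidence and timing.

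The stronger conclusion, that the trial's safety comparison is invalid or materially distorted, is not supported. Kaplan-Meier is suitable for all-cause mortality, and the primary outcome is not touched by this point. The reason to act is that the two routes target different quantities and the named method does not estimate the stated outcome, while the correction is simple.

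**What to change.** In the Analysis section, keep Kaplan-Meier and Cox regression for all-cause mortality. For VTE, MI, CVA and wound complications, specify six-month cumulative incidence per arm by the Aalen-Johansen estimator, with death as a competing event, and report the between-arm risk difference with 95% CI. Label any hazard ratio cause-specific and read it alongside mortality by arm. With no losses, Aalen-Johansen equals the simple proportion, so both routes then estimate the same quantity.

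The cost is a sentence or two of text and minor extra analysis in standard software. No added patients or visits are needed: mortality is already an outcome to six months, and the planned survival methods already need event and death times. Reported event rates will be slightly lower. Like Kaplan-Meier, the estimator assumes that loss to follow-up is unrelated to event risk, so the change does not correct for informative loss.

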### Sample Size

In a prospective randomized, controlled trial conducted in Denmark evaluating a similar outcome in the same patient population, there was a transfusion rate of 84.6% in the control group, who never received

TXA [9]. However, a retrospective evaluation of the transfusion rate for the population of interest at our institution in 2014 with standard transfusion thresholds as reflected in the above described protocol was 50%. Utilizing this transfusion rate, the sample size was calculated to be able to detect a difference of 50% versus 25% (a reduction of risk by 1/2) between the control group and treatment group, respectively. A sample of 58 subjects per study group (116 in total) will provide 80% power to detect a difference in the proportion of patients receiving blood transfusion of 50% versus 25% ( $\alpha=0.05$ , two-sided test) [10]. We will assume an attrition rate of at least 15%, thus the target sample size will be 78 patients per group, 156 in total.

